#### **17.4. Protocol Amendments and Emergency Deviations**

All revisions and/or amendments to this protocol must be approved in writing by the Sponsor and the appropriate IRB/IEC. The Investigator will not make any changes to the conduct of the study or the protocol without first obtaining written approval from the Sponsor and the IRB/IEC, except where necessary to eliminate an apparent immediate hazard to a study subject.

Emergency deviations or modifications must be reported to the Sponsor/CRO and the IRB/IEC within five business days of the occurrence, or in accordance with applicable regulatory requirements.

#### **17.5. Financial Disclosure**

By signing this protocol, the Investigator agrees to provide to the Sponsor prior to start of study accurate financial information to allow the Sponsor to submit complete and accurate certification and disclosure statements as required by the US FDA regulations (21 CFR Part 54). The Investigator further agrees to provide this information on a Financial Disclosure/Certification Form that is provided by the Sponsor. The Investigator will update this information if there are any relevant changes during the conduct of the study and for one year after completion of the study.

The Investigator also consents to the transmission of this information to the Sponsor for these purposes. This may involve the transmission of information to countries that do not have laws protecting personal data.

#### **17.6. Publication Policy**

Any formal presentation or publication of data collected as a direct or indirect result of the study will be considered a joint publication by the Investigators and the appropriate personnel of the Sponsor. For multicenter studies, it is mandatory that the first publication is based on all data obtained from all analyses as stipulated in the protocol. Investigators participating in multicenter studies must agree not to present data gathered individually or by a subgroup of centers before the full, initial publication, unless this has been agreed to by all other Investigators and by the Sponsor.

RCT	Randomized Controlled Trials
SCR	Screening
SAE	Serious Adverse Event
SAD	Social Anxiety Disorder
TEAE	Treatment Emergent Adverse Events

FDA	U.S. Food and Drug Administration
UADE	Unanticipated Adverse Device Effects
VR	Virtual Reality
VRET	Virtual Reality Exposure Therapy
V	Visit
W	Week

2 Introduction

This statistical analysis plan (SAP) provides the detailed methodologies and statistical analyses of the data collected in the study BVR100-102 associated with protocol version 1.00 (dated 21-JUN-2023) and Electronic Case Report Form (eCRF) version 2.0 (date: 20-SEP-2023). This document may modify the plans outlined in the protocol; however, any major modifications of the study endpoints definition or the analysis will also be reflected in a protocol amendment. If a discrepancy is found between the description in the statistical section of the protocol and this document, the description in this document supersedes the descriptions in the statistical section of the protocol. Any deviations from the final analysis plan or from what is outlined in the protocol will be discussed in the final study report.

The SAP includes prespecified analyses of all data from each subject through the End of Study (EOS) or Early Termination (ET). The EOS is defined as the time at which subjects completed all study visits, have failed screen, are lost to follow-up, have withdrawn of consent for further participation in the study, have adverse event, including Unanticipated Adverse Device Effects (UADE), have protocol deviation or death, or other reasons. ET is defined as the time subjects who prematurely discontinue from the study.

2.1 Background

Social anxieties and fears exist along a continuum of intensity, ranging from mild phenomena such as shyness to psychopathological levels of fear and anxiety that can be classified as social anxiety disorder (SAD) [1]. SAD is characterized by overwhelming anxiety and excessive self-consciousness in everyday social situations, which causes significant distress and often leads to impairment in important areas of functioning [2].

SAD can be a chronic and naturally unremitting disorder if not treated adequately. Despite the extent of suffering and impairment, only about half of adults with the disorder ever seek treatment. Guidelines from the National Institute for Health and Care Excellence recommend individual Cognitive Behavioral Therapy (CBT) as the first-line treatment for adults with social anxiety [4].

Virtual reality (VR) technology offers a unique opportunity to disseminate CBT and exposure therapy. Studies indicate that patients prefer to receive VR exposure therapy (VRET) to traditional exposure therapy [5]. Because of its potential to shield subjects' attention from distraction and induce strong feelings of presence, VR can enhance the practices of mindfulness and facilitate emotion regulation therefore reducing symptoms of anxiety. Furthermore, VR may be combined with engaging game-design mechanics to deliver highly automated unguided interventions, thus showing an enormous potential for improving public health due to its cost-effectiveness and scalability.

The current study will test BVR-100, a VR-based multi-session, self-led intervention for social anxiety symptoms including CBT techniques against BES-100, a VR-based intervention intended as a control-arm for BVR-100.

2.2 Rationale

Digital therapeutics (DTx) are evidence-based software products used to prevent, manage, or treat medical conditions. DTx need to adhere to the same standards of evidence and regulatory oversight as

prescription medications and traditional medical devices. However, DTx face additional challenges to establishing appropriate control conditions that support evidence generation in randomized controlled trials (RCT). In particular, DTx interventions are subject to “digital placebo” effects, involving technology-related non-specific effects (e.g., beliefs about technology, design of the hardware and software, information provided, medium of delivery, Time-on-Task, etc.), that are not present in drug trials. Furthermore, DTx delivering psychological interventions such as CBT are faced with the additional challenge of controlling for more complex placebo effects that typically occur in the context of psychotherapy, such as the effect of the frequency and intensity of therapist–patient interactions. While the FDA acknowledges that “it may be challenging to construct a placebo control that appears to function like the investigational device but delivers no therapy” (Center for Devices & Radiological Health, n.d.), it is still recommended that Sponsors evaluate placebos in terms of their face-validity (i.e., Time-on-Task), blinding, and subject retention. Pilot testing BVR-100 against a “sham” control such as BES-100 will provide the Sponsors with the opportunity to test the face-validity of the BES-100, preliminarily assess the effectiveness of BVR-100 and BES-100, and inform the subsequent large-scale RCT.

3 Study Objectives

The objective of this study is to compare two Virtual Reality (VR)-based interventions, BVR-100 and BES-100, for the treatment of Social Anxiety Disorder (SAD).

3.1 Primary Objective

The primary objective of this study is to evaluate the credibility and expectation of benefit of BVR-100 and BES-100 for subjects with SAD, as measured with the Credibility/Expectancy Questionnaire (CEQ).

3.2 Secondary Objective

The secondary objective of this study is to evaluate subject retention and Time-on-Task of BVR-100 and BES-100.

3.3 Exploratory Objectives

This study will pursue the following exploratory objectives:

- *To explore subjects’ experiences and acceptability of BVR-100 and BES-100 in a Qualitative Interview.*
- *To evaluate the therapeutic response of the two interventions for SAD on:*
 - *Fear and avoidance symptoms, as measured by the clinician administered Liebowitz Social Anxiety Scale (LSAS).*
 - *Overall symptomatology and functioning, using the Clinical Global Impression Severity scale (CGI-S), the Clinical Global Impression Improvement scale (CGI-I), and the Patient Global Impression Improvement scale (PGI-I).*
 - *Depression symptoms, measured with the Patient Health Questionnaire (PHQ-9).*
 - *To evaluate the number of required sessions completed during the study.*

3.4 Safety Objectives

This study will evaluate the safety of BVR-100 and BES-100, as measured by:

- *Incidence of adverse events (AEs),*
- *Incidence of serious adverse events (SAEs),*
- *Incidence of unanticipated adverse device effects (UADEs), and*
- *The Columbia Suicide Severity Rating Scale (C-SSRS).*

4 Study Design

4.1 Overview

This is a parallel-group, double-blind, randomized, controlled, decentralized, study. The aim of the study is to evaluate the credibility and acceptability, subject retention, and Time-on-Task of BVR-100 and BES-100 in a sample of subjects with Social Anxiety Disorder (SAD).

The study will include 3 periods as shown in table below.

SCR	RND	Intervention Period (Double-Blind)					
		BSL / W1	W2	W4	W6	W8/EOS/ET	
V1	V2	V3	V4	V5	V6	V7	
Up to 14 days	Up to 7 days	Days 1-7	Days 8-14	Days 22-28	Days 36-42	Days 50-56	

Abbreviations: SCR = Screening; RND = Randomization; BSL = baseline; EOS = End of Study; ET = Early Termination; V = telehealth / call visits; W = week.

The total study duration will be approximately 11 weeks from Screening through EOS (Week 8).

4.2 Sample Size Justification

Due to the pilot nature of the study, no formal sample size calculations will be conducted. However, fifteen people per arm are recommended. In order to account for a possible attrition rate of 25%, twenty people per arm (total n = 40) will be recruited. In order to ensure adequate data for evaluation, early discontinued subjects may be replaced at Sponsor discretion.

4.3 Randomization and Blinding

Randomization will occur after confirmation of eligibility and continued subject interest are verified. Subjects will be randomly allocated to either the treatment group (BVR-100) or the control (BES-100) group. Randomization will be assigned via an interactive web responses system (IWRS) in a 1:1 ratio to either BVR-100 or to BES-100.

Once a randomization number has been assigned, it cannot be reused. The randomization schedule will be generated by an independent, non-study biostatistician.

Subjects, Investigators, investigator site staff, persons performing the assessments, clinical operations personnel, data analysts and Sponsor, will remain blinded to the identity of the VR intervention from the time of randomization until database lock and unblinding.

4.4 Inclusion/Exclusion Criteria

For details of Inclusion/Exclusion criteria, please refer to the protocol section 1 – Inclusion and Exclusion Criteria.

4.5 Treatment Allocation

Subjects will be assigned via an IWRS in a 1:1 ratio to either BVR-100 or to BES-100. A VR headset pre-loaded with either BVR-100 or BES-100 will be shipped to the subject's address.

BVR-100 is a non-invasive, self-guided, at-home, VR intervention which offers educational modules and immersive environments created using both computer-generated and 360° videos. The intervention includes immersive and automated VR experiences that guide the user through educational and experiential learning modules.

BES-100 is a non-invasive, self-guided, multisession, at-home, VR intervention designed to be used as a sham control condition for the evaluation of BVR-100 in the treatment of SAD. BVR-100 and BES-100 are comparable in all technological, design, and programmatic characteristics, except for the mechanisms of action. The computer-generated environment will be interactive to increase engagement and provide subjects with a similar interactive experience as BVR-100.

Both are intended as an 8-week program with a recommended minimum frequency of 3 weekly sessions. Each session will be approximately 5-20 minutes long (depending on type and amount of content experienced).

5 Assessment Schedule

Study Period	Screening	Randomization	Investigational Intervention Use Period				
			Baseline ^a	V4	V5	V6	V7
Study Visit	V1	V2	V3	V4	V5	V6	V7
Study Week	NA	NA	W1	W2	W4	W6	W8 (EOS/ET) ^b
Study Visit Days	Up to 14 days	Up to 7 days	1-7	8-14	22-28	36-42	50-56
Procedure							
Obtain Informed Consent	X						
Review Inclusion/Exclusion Criteria	X	X					
Record Demographics and Baseline Characteristics	X						
Record Medical/ Psychiatric History	X						
Administer MINI	X						
Randomization ^c		X					
Dispense Investigational Intervention via IWRS ^c		X					
Subject Self-guided Weekly VR Sessions ^d			X	X	X	X	X
Clinician Administers the LSAS	X		X	X	X	X	X
Clinician Administers the C-SRSS	X		X		X		X
Subject Completes the PHQ-9 ^e	X		X	X	X	X	X
Subject Completes the CEQ			X			X	X
Clinician Administers the CGI-I				X	X	X	X
Clinician Administers the CGI-S			X	X	X	X	X
Subject Completes the PGI-I				X	X	X	X
Conduct Qualitative Interview ^f							X
Prior/Concomitant Medications	X	X	X	X	X	X	X
Pretreatment Event and Adverse Event Monitoring	X	X	X	X	X	X	X
Subject Returns Investigational Intervention ^f							X
Telephone Contact ^g	X	X	X	X	X	X	X

Abbreviations: AE = Adverse Event; CEQ = Credibility/Expectancy Questionnaire; D = Day; EOS = End of Study; ET = Early Termination; C-SRSS = Columbia Suicide Severity Rating Scale; MINI = Mini-International Neuropsychiatric Interview; CGI-I = Clinical Global Impression – Improvement scale; CGI-S = Clinical Global Impression – Severity scale; LSAS = Liebowitz Social Anxiety Scale; PGI-I = Patient Global Impression – Improvement scale; PHQ-9 = Patient Health Questionnaire; PROs = Patient-Reported Outcomes VR = Virtual Reality; W = Week.

^a The Baseline visit should be scheduled within 5-7 days of the Randomization visit. The Baseline visit will consist of two parts. The first part will be conducted by investigator site staff via a telehealth call and will include the administration of clinician-administered outcome measures, collection of AEs, concomitant medication, and delivery of the PHQ-9. The second part will be self-administered by the subject and will include the video-guided VR onboarding session, the first self-guided VR session, and the completion of the CEQ.

^b For subjects who prematurely discontinue from the study, every effort should be made to complete the final evaluation procedures at the Early Termination (ET) visit within 5 days of the last exposure to the Investigational Intervention, including the PROs if they have not been completed by the subject for the given week.

^c Randomization cannot occur until the subject has been deemed eligible by the site and Inclusion and Exclusion criteria re-confirmed with the subject via a telehealth contact and after subject interest to participate in this study is confirmed. Upon Randomization using the IWRS, the Investigational Intervention shipment to the subject will be initiated.

^d The subject self-guided weekly VR sessions begin after the first part of the Baseline visit is completed. During weeks 2, 4, 6 and 8, 3 required VR sessions should be completed prior to the PROs. In addition to the required practices, subjects will be encouraged to also engage with optional content and to review content completed in previous sessions.

^e The PROs will be completed by the subject during the Telehealth contact, for Screening and Baseline Visits, as applicable, in an unassisted manner. During Weeks 2, 4, 6, and 8, these are to be completed after the self-guided at home VR sessions.

^f The W8/EOS/ET assessments will consist of three parts. The first part will be the Subject's at home completion of the required 3 VR modules and electronic PRO assessments. The second part will include the telehealth visit with the investigator site staff to complete all applicable assessments. The third part will be conducted by the unblinded site support team where the Qualitative Interview will be completed as the final study assessment on the same day or within 48 hours. During this visit, the unblinded site support team will instruct the subject to return the device and provide any necessary guidance.

^g The Telehealth contact during weeks 2, 4, 6, and 8, to collect concomitant medication and/or AEs, clinician administered C-SRSS, LSAS, CGI-S, CGI-I, and other applicable assessments, should be completed on the last 3 days of each week. At any point in the study, an unscheduled Telehealth contact can be performed if requested by the investigator site staff/subject.

6 Interim Analysis

There is no interim analysis planned for this study.

7 Efficacy and Safety Endpoints

7.1 Primary Endpoint

The primary endpoint of this study is the measurement of intervention credibility and expectancy of benefit, assessed with the Credibility / Expectancy Questionnaire (CEQ) scores, at Baseline, Week 6, and Week 8/EOS.

7.2 Secondary Endpoints

Secondary endpoints for this study include:

- Subject retention in each group will be assessed by percentage of subjects who remain on the study at Week 6, and Week 8/EOS.
- Time-on-Task, averaged over all VR sessions, will be assessed at Week 6 and Week 8/EOS. Time-on-Task will be automatically recorded by the VR system after each session.

7.3 Safety Endpoints

- Incidence of AEs.
- Incidence of SAEs.
- Incidence of UADEs.
- Frequency of subjects with suicidal ideation or suicidal behavior based on the C-SSRS.

7.4 Exploratory Endpoints

- The overview of qualitative input obtained during Qualitative Interviews at Week 8.
- The mean change from baseline in LSAS scores at Week 2, Week 4, Week 6, and Week 8.
- The proportion of “responders”, that is, subject who are rated 1 (very much improvement) or 2 (much improvement) in the CGI-I at end-of-treatment (Week 8).
- The mean change from baseline in CGI-S score at Week 2, Week 4, Week 6, and Week 8.
- The mean PGI-I score at Week 2, Week 4, Week 6, and Week 8.
- The mean change from baseline in PHQ-9 score at Week 2, Week 4, Week 6, and Week 8.
- The number of VR sessions completed during the study.

8 Statistical Methods

8.1 General Conventions

Level of significance for statistical tests will be 0.05 two-sided. All analyses will be done using SAS (version 9.4, SAS Institute Inc., Cary, NC, USA).

Safety endpoints will be analyzed in a descriptive manner. Continuous data will be reported using the following descriptive statistics:

- Number of observations (n)
- Mean and Standard deviation (SD)
- Median
- Minimum (min) and Maximum (max)
- 25th percentile and 75th percentile

Categorical data will be presented using frequency (n = number of subjects; m = number of events) and percentage (%).

Listings will be provided for all data recorded in eCRF to study subject profiles. All listings will be sorted by treatment, subject ID and date (if applicable). Unscheduled visit data will only be listed and not included in summaries.

All p-values will be displayed to four decimal places, with p-values less than 0.0001 presented as '<0.0001' and p-values greater than 0.9999 presented as '>0.9999'. Minimum and maximum values will be reported in the units of collection with 3 decimals being maximum value; the mean, median, 25th percentile and 75th percentile will be presented with 1 decimal place more and the standard deviation 2 decimal places more than the units of collection. Percentages for categorical summaries will be represented to 1 decimal place.

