##### ***PART 2 (investigator site staff during telehealth Visit 4 (W2)/ Visit 5 (W4) / Visit 6 (W6)/ Visit 7 (W8/EOS)):***

During the last 3 days of Weeks 2, 4, 6, and 8, the investigator site staff will conduct telehealth study visits to complete the following assessments:

- Clinician administers C-SSRS. (Week 4 and Week 8 ONLY)
- Clinician administers LSAS.
- Clinician completes CGI-S.
- Clinician completes CGI-I.

- Collect AEs and concomitant medication changes.

All attempts will be made to ensure that each subject is assessed by the same study staff to minimize confounding bias due to changing assessors.

Unscheduled telehealth visits to complete/perform additional safety assessments, may be conducted as deemed necessary by the investigator site staff/subject.

After the completion of the telehealth portion of visit 7 with investigator site staff, the second part of the visit will be conducted separately by a member of the unblinded site support team where the Qualitative Interview will be completed as the final study assessment on the same day or within no later than 48 hours. During this visit, the unblinded site support team will instruct the patient to return the device and provide any necessary guidance/instructions.

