#### **15.4.3.2 Suicidality Measure**

Frequency and severity of suicidal ideation and suicidal behavior as measured by the C-SSRS scale will be summarized by treatment for the overall post-Baseline period and by visit.

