11.3 Analysis Visits

All analysis datasets with measurements taken at more than one visit/time point will have analysis visit and timepoint as defined below.

Collected Visit	Analysis Visit
Screening	Visit 1 Screening
Randomization	Visit 2 Randomization
Week 1	Visit 3 Week 1
Week 2	Visit 4 Week 2
Week 4	Visit 5 Week 4
Week 6	Visit 6 Week 6
Week 8/ End of Study/ Early Termination	Visit 7 Week 8

A subject is considered to have attended any visit only if at least one assessment has been taken at the visit. As per section 11.10, derived baseline results will also be presented in summary tables.

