11.3.1 Repeat Assessments

For safety and efficacy endpoints, if an unscheduled visit occurred on the same day as the scheduled visit, then it will be considered as a repeat for that assessment. Repeat and Unscheduled visits will not be considered for summary purpose but will be included in listing and baseline calculation.

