11.16 Columbia-Suicide Severity Rating Scale (C-SSRS)

The following outcomes are C-SSRS categories. The categories have been re-ordered from the actual scale to facilitate the definition of composite endpoints:

Category 1	Wish to be Dead
Category 2	Non-Specific Active Suicidal Thoughts
Category 3	Active Suicidal Ideation with Any Methods (Not Plan) without Intent to Act
Category 4	Active Suicidal Ideation with Some Intent to Act, without Specific Plan
Category 5	Active Suicidal Ideation with Specific Plan and Intent
Category 6	Actual Attempt
Category 7	Has subject engaged in Non-Suicidal Self-Injurious Behavior?
Category 8	Interrupted Attempt
Category 9	Aborted Attempt
Category 10	Preparatory Acts or Behavior

Suicidal Ideation – A “yes” answer at a visit to any one of the 5 suicidal ideation questions (categories 1-5) on the C-SSRS.

Suicidal Behavior – A “yes” answer at a visit to any one of the 5 suicidal behavior questions (categories 6-10) on the C-SSRS.

Suicidal Ideation or Suicidal Behavior – A “yes” answer at a visit to any one of the questions on the C-SSRS.

It is possible for subjects to have neither suicidal ideation nor suicidal behavior, or even to have both suicidal ideation and suicidal behavior.

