12.10.5 Columbia- Suicide Severity Rating Scale (C-SSRS)

Number and percentage of subjects without suicidal ideation or suicidal behavior, with suicidal ideation, with suicidal behavior, and with suicidal behavior or ideation will be presented by treatment groups based on ITT Population. All C-SSRS data will be listed based on all Enrolled population.

Above analysis details are specified in DDP Table 14.3.3.1 and Listing 16.2.8.1.

13 Changes to Planned Analyses

- 1 Protocol (section 12.3) specifies 'Baseline demographic and clinical characteristics will be compared between groups with the use of the two-sample t-test and the Mann–Whitney test for continuous measurements with and without normal distribution, respectively'. But the statistical testing for baseline characteristics is being waived as per the recent discussion with the sponsor.
- 2 Protocol (section 12.9) mentions an analysis about differences in the mean change from CGI-S baseline score in the CGI-I and PGI-I at Weeks 2, 4, 6, and 8. This analysis is waived as per the recent discussion with sponsor.
- 3 An additional exploratory endpoint number [7](#) regarding the number of required BVR-100 and BES-100 sessions completed, is added in the section 7.4 as per the decision by sponsor clinical team.
- 4 Sentence "to ensure a reliable estimate of the standard deviations to power a future trial with 90% and an expected effect size between 0.3 and 0.7" in section 4.2 Sample Size Justification is removed because it is for future study not for this current study.
- 5 Per-protocol population definition in section 10.5 is updated to consider only ITT population as per the recent discussion with sponsor.
- 6 Baseline clinical characteristics is updated to follow the baseline definition in section 11.10 as per the recent discussion with sponsor.
- 7 In section 10.4, mITT (Modified Intent-to-Treat) population is removed from analysis and ITT population (efficacy population) has been added as per sponsor request. This population will be used for primary and secondary endpoint analysis.

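### SAP 8.1 and 11.3.1 keep post-Baseline unscheduled and repeat C-SSRS forms out of the summary table, and 12.10.5 makes no exception, so a subject positive only on such a form is listed but not counted

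*SAP*

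**What the plan says.** **The general rule.** SAP 8.1: "Unscheduled visit data will only be listed and not included in summaries". SAP 11.3.1 first defines a repeat, for safety as well as efficacy endpoints, as an unscheduled visit on the same day as a scheduled one. It then says: "Repeat and Unscheduled visits will not be considered for summary purpose but will be included in listing and baseline calculation". SAP 11.3 adds: "All analysis datasets with measurements taken at more than one visit/time point will have analysis visit and timepoint as defined below". The table that follows it has only Visits 1 to 7.

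**The endpoint and its table.** SAP 7.3 lists as a safety endpoint: "Frequency of subjects with suicidal ideation or suicidal behavior based on the C-SSRS". SAP 11.16 counts as ideation a positive answer at a visit to "any one of the 5 suicidal ideation questions (categories 1-5) on the C-SSRS", so Items 1 to 3 count as well as Items 4 and 5. SAP 12.10.5 tabulates, by treatment group, "Number and percentage of subjects without suicidal ideation or suicidal behavior", followed by those with ideation, with behavior, and with either. It also lists all C-SSRS data. It says nothing about unscheduled or repeat forms.

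**The protocol.** Section 15.4.3.2 says that the C-SSRS results "will be summarized by treatment for the overall post-Baseline period and by visit". Section 11.5.4, Part 2, provides: "Unscheduled telehealth visits to complete/perform additional safety assessments, may be conducted as deemed necessary by the investigator site staff/subject". Section 11.5.5 says the same for Weeks 3, 5 and 7. After Baseline the C-SSRS is scheduled only at Week 4 and at Week 8 or early termination.

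**The concern.** The endpoint counts subjects, not scheduled visits. A visit called because someone is worried about a subject is a plausible place for suicidal ideation to surface. Under the general rule, a positive C-SSRS from such a visit cannot enter the table that reports this endpoint. Unless a scheduled or early-termination form is also positive, the subject falls into the row for those with neither ideation nor behavior, while the listing shows the opposite.

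The C-SSRS frequency is the trial's only suicidality endpoint. In a study of this size, one subject can decide whether the table reads none or one. SAP section 13 lists seven changes to the planned analyses, and limiting the C-SSRS counts to scheduled forms is not among them.

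**Working it through.** The plan states no figure for this point, so the check traces one subject through the rules and then sizes a single missed case.

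**1. Which forms reach the table?**
- Scheduled Week 4 and Week 8 forms: yes (SAP 11.3 and 12.10.5).
- Early-termination forms: yes. SAP 11.6 summarizes them with Week 8.
- Unscheduled forms after Baseline: no (SAP 8.1 and 11.3.1).
- Same-day repeat forms after Baseline: no (SAP 11.3.1).
- Unscheduled or repeat forms before Baseline: they may feed the baseline value (SAP 11.3.1 and 11.10), so the gap is post-Baseline only.

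SAP 11.16 and 12.10.5 were checked for an exception, and there is none.

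**2. Can a C-SSRS be given at an unscheduled visit?** This is an inference. Protocol 11.5.4 and 11.5.5 allow additional safety assessments without naming them. Section 11.4 has two subsections, adverse events and the C-SSRS. On the other side, Section 11.4 ties safety assessments to Table 2, which has no unscheduled column. It is permitted, but not established that it happens.

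**3. What else could catch the case?**

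| Route | What it catches | What it leaves |
|---|---|---|
| Mandatory AE, Protocol 11.4.2 | Item 4 or 5 on any post-Baseline C-SSRS | Items 1–3; the C-SSRS table itself is unchanged |
| Ordinary AE reporting, Protocol 11.4.1 and 12.1.1 | May catch Item 1–3 ideation; the AE tables are not tied to analysis visits | Not stated as mandatory for Items 1–3 |
| Early-termination form, SAP 11.6 | Subjects who stop | Item 1–3 ideation does not force discontinuation |
| Next scheduled form (Since Last Visit version) | Ideation that persists past the unscheduled visit and is reported again | Ideation that has ended, depending on which visit the form looks back to; Protocol 11.4.2 does not say |
| PHQ-9 at Weeks 2, 4, 6 and 8, reviewed for AEs (Protocol 11.5.4) | May prompt an AE | SAP 11.17.7 derives only the total, so item 9 is not summarized |

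What remains is mainly Item 1–3 ideation that is not reported as an AE and not elicited again on a scheduled or early-termination form.

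**4. Size of one missed subject.** Input: 52 subjects in the Safety Population, all of them in the ITT population (SAP section 13, January 2024 data cut). Assumption: 26 per arm, with 24 to 28 as a range, because the split is not given.
- Change in an arm's rate = 1/n: 1/24 = 4.2%, 1/26 = 3.8%, 1/28 = 3.6%.
- Change in the pooled rate: 1/52 = 1.9%.
- Exact (Clopper–Pearson) 95% intervals: 1/26 gives 0.1% to 19.6%; 0/26 gives 0% to 13.2%.

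The number of unscheduled or repeat C-SSRS forms is not in the documents. If there are none, the effect is zero.

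**The case against.** The strongest reply has five parts.

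- **The premise is unproven.** No text places the C-SSRS at an unscheduled visit, and Protocol 11.4 refers safety assessments to Table 2. This stands, so the point has to be conditional.
- **Adverse-event reporting already covers most of it.** Protocol 11.4.2 describes the C-SSRS as tracking suicidal adverse events, ideation included. Exclusion criterion 9 removes people with recent active ideation, so active ideation after Baseline would usually be new or worsened. AEs are collected at every scheduled contact and by spontaneous report. This largely stands and keeps the impact low, but an AE row does not correct the C-SSRS table.
- **There is no formal conflict.** The SAP says that it supersedes the protocol's statistical section, and a count from scheduled forms is still based on the C-SSRS. It stands that the SAP governs. What remains is that the count is narrower than the protocol's overall post-Baseline summary and that section 13 does not say so.
- **Nothing is hidden.** All C-SSRS data are listed and the safety analysis is descriptive. This also stands.
- **Scheduled-only counts give both arms the same opportunity to be positive.** Unscheduled visits are triggered by staff or subject, so ascertainment could differ between arms. This is a small, real downside. It is met by keeping scheduled-visit rows beside the any-time count.

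A reader might infer that ideation found at an unscheduled visit is lost to every later form, because later forms ask only about the time since the last visit. The documents do not support that. Persisting ideation can be captured on the next scheduled form, and the visit to which that form looks back is not defined. No share of cases lost can be calculated, because the documents give neither how long ideation lasts nor how often it is reported again.

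**Conclusion.** The point holds as a conditional gap. As written, the SAP would tabulate a subject whose only positive post-Baseline C-SSRS is on an unscheduled or repeat form as having neither ideation nor behavior. That is narrower than a subject-level endpoint calls for.

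The importance is low and the effect may be nil. The 3.8-point illustration rests on one such subject and an assumed 26 per arm; it is not an estimate of bias. The shell of Table 14.3.3.1 is in the Data Display Plan, which is not among the documents, so an exception or an overall row there cannot be ruled out. The documents do not support reading this as known under-reporting of suicidality in the trial. It is a cheap improvement.

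**What to change.** Add one sentence to SAP 12.10.5: as an exception to 8.1 and 11.3.1, subject-level counts of suicidal ideation and behavior at any time post-Baseline use every post-Baseline C-SSRS assessment, whether scheduled, unscheduled, repeat or early termination. Keep by-visit rows to scheduled visits, with early termination under Week 8 as now, so that the arms can still be compared on equal ascertainment.

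The cost is that sentence, plus one row in Table 14.3.3.1 if its shell lacks an any-time post-Baseline count. The data are already listed. No extra visit or protocol amendment is needed, since the change restores the summary in Protocol 15.4.3.2. If no unscheduled or repeat forms exist, no count changes.
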